6.7. Continued Access to Study Intervention After the End of the Study

No study intervention will be provided to participants at the end of their study participation. It is expected that participants will be treated as required with standard-of-care treatments, as advised by their usual care physician.

6.8. Treatment of Overdose

For this study, any dose of study intervention greater than the maximum dose of study intervention according to the protocol within a 24-hour time period will be considered an overdose.

There is no specific treatment for an overdose.

In the event of an overdose, the investigator/treating physician should:

1. Contact the study medical monitor within 24 hours.
2. Closely monitor the participant for any AEs/SAEs and laboratory abnormalities as medically appropriate and at least until the next scheduled follow-up.

3. Document the quantity of the excess dose as well as the duration of the overdose in the CRF.
4. Overdose is reportable to the sponsor **only when associated with an SAE**.
5. Obtain a blood sample for PK analysis as soon as overdose is identified but no later than 24 hours from the last over-dosed study intervention if requested by the study medical monitor (determined on a case-by-case basis).

Decisions regarding dose interruptions or modifications will be made by the investigator in consultation with the study medical monitor as needed based on the clinical evaluation of the participant.

6.9. Prior and Concomitant Therapy

All participants are required to maintain stable dosing of permitted prescribed and OTC medications for the duration of the study.

6.9.1. Prohibited During the Study

The following therapies are prohibited during the study:

- Any additional therapies to treat CeD.
- Other investigational agents, including biologic or non-biologic immunosuppressive or immunomodulatory therapies.
- Non-investigational systemic immunosuppressive and immunomodulatory therapies (eg, systemic corticosteroids).
- All vaccines between 4 weeks prior to dosing through 4 weeks from the last dose of study intervention; vaccines are permitted at all other times during the study.

6.9.2. Permitted During the Study

Hormonal contraceptives that meet the requirements of this study are allowed to be used in participants who are WOCBP (see [Appendix 4](#)).

HRT use by postmenopausal women is permitted if they meet requirements in [Appendix 4](#).

Any other medication that is considered necessary for the participant's welfare that is not expected to interfere with the evaluation of KAN-101 may be given at the discretion of the investigator and documented on the CRF.

In cases involving concomitant therapies whose predicted interference with KAN-101 is unknown to the investigator, the sponsor should be contacted for discussion.

Any medication (including over the counter or prescription medications, vitamins, and/or herbal supplements) that the patient receives after enrollment through the last study visit

must be recorded on the CRF. Participants should report any changes to permitted medications during the study to the investigator as soon as they occur. Medication changes must be documented in the participant's record and CRF.

Patients being treated for IBS symptomology will be allowed to continue therapy (eg, dicyclomine) unless the drug is specifically prohibited.

Antidiarrheal (eg loperamide) or antiemetics (eg metoclopramide or ondansetron) may be used for IBS symptomatic treatment if warranted by symptomology unless the drug is specifically prohibited. If given at a study visit, use must be recorded on the CRF.

6.9.3. Rescue Medicine

There is no rescue therapy to reverse AEs observed with KAN-101; standard medical supportive care, (such as ondansetron) may be provided to manage AEs.

Medication such as Ondansetron is:

Part A: allowed in as symptomatic treatment,

Part B and Part C: allowed as symptomatic treatment of an AE after study drug intervention; and optionally allowed as pre-treatment to subsequent study intervention administration at investigator discretion based on the occurrence of AEs after previous study drug administration.

7. DISCONTINUATION OF STUDY INTERVENTION AND PARTICIPANT DISCONTINUATION/WITHDRAWAL

7.1. Discontinuation of Study Intervention

It may be necessary for a participant to permanently discontinue study intervention. Reasons for permanent discontinuation of study intervention include the following:

- An AE that requires permanent discontinuation of study treatment*;
- Noncompliance with the protocol;
- Investigator decision;
- Participant becomes pregnant;
- Participant death;
- Participant lost to follow-up;
- Termination of the study by the sponsor;

- Voluntary withdrawal of consent by the participant.

* Note: AEs leading to the discontinuation of study intervention will be followed until resolution, resolution to baseline, or the event is considered stable or chronic.

Note that discontinuation of study intervention does not represent withdrawal from the study. If study intervention is permanently discontinued, the participant should remain in the study to be evaluated for safety. See the [SoA](#) for data to be collected at the time of discontinuation of study intervention and follow-up for any further evaluations that need to be completed.

In the event of discontinuation of study intervention, it must be documented on the appropriate CRF/in the medical records whether the participant is discontinuing further receipt of study intervention or also from study procedures, posttreatment study follow-up, and/or future collection of additional information.

Participants who withdraw from treatment and do not receive 3 full doses should not receive the GC or have plasma samples taken for IL-2 on GC days.

7.1.1. Liver Injury

A participant who meets the criteria as described in [Appendix 6](#) will be withdrawn from study intervention.

7.1.2. Pregnancy

Pregnancy tests are conducted as specified per the [SoA](#) and administration of study intervention or GC will occur only in the presence of a negative pregnancy test.

If a participant is confirmed to be pregnant (see [Section 8.3.6](#)) during any visit, conducting of GCs and further dosing with study intervention will be discontinued immediately and permanently.

[Section 8.4.5.1](#) describes the follow-up activities if a participant meets EDP criteria.

7.1.3. COVID-19

If a participant has COVID-19 during the study, this should be reported as an AE or SAE (as appropriate) and appropriate medical intervention provided.

It is recommended that the investigator discuss temporary or permanent discontinuation of study intervention with the study medical monitor.

7.1.4. Temporary Discontinuation

In cases where a temporary discontinuation or dosing interruption is required, the total infusion should be completed within 6 hours of thawing the drug product. Any temporary discontinuations or interruptions of study intervention should be documented in the CRF.

See [Appendix 9](#) for detailed guidance regarding infusion administration interruptions due to IRR.

7.2. Participant Discontinuation/Withdrawal From the Study

A participant may withdraw from the study at any time at their own request. Reasons for discontinuation from the study include the following:

- Investigator's decision;
- Participant death;
- Participant lost to follow-up;
- Termination of the study by Sponsor;
- Voluntary withdrawal of consent of participant.

At the time of discontinuing from the study, if possible, an early discontinuation visit should be conducted. See the [SoA](#) for assessments to be collected at the time of study discontinuation and follow-up and for any further evaluations that need to be completed.

The participant will be permanently discontinued from the study intervention and the study at that time.

If a participant withdraws from the study, they may request destruction of any remaining samples taken and not tested, and the investigator must document any such requests in the site study records and notify the sponsor accordingly.

If the participant withdraws from the study and also withdraws consent (see Section 7.2.1) for disclosure of future information, no further evaluations will be performed and no additional data will be collected. The sponsor may retain and continue to use any data collected before such withdrawal of consent.

7.2.1. Withdrawal of Consent

Participants who request to discontinue receipt of study intervention will remain in the study and must continue to be followed for protocol -specified follow-up procedures. The only exception to this is when a participant specifically withdraws consent for any further contact with them or persons previously authorized by the participant to provide this information. Participants should notify the investigator in writing of the decision to withdraw consent from future follow-up, whenever possible. The withdrawal of consent should be explained in detail in the medical records by the investigator, as to whether the withdrawal is only from further receipt of study intervention or also from study procedures and/or posttreatment study follow-up, and entered on the appropriate CRF page. In the event that vital status (whether the participant is alive or dead) is being measured, publicly available information should be used to determine vital status only as appropriately directed in accordance with local law.

7.3. Lost to Follow-Up

A participant will be considered lost to follow-up if the participant repeatedly fails to return for scheduled visits and is unable to be contacted by the study site.

The following actions must be taken if a participant fails to return to the clinic for a required study visit:

- The site must attempt to contact the participant and reschedule the missed visit as soon as possible. Counsel the participant on the importance of maintaining the assigned visit schedule, and ascertain whether the participant wishes to and/or should continue in the study;
- Before a participant is deemed lost to follow-up, the investigator or designee must make every effort to regain contact with the participant (where possible, 3 telephone calls and, if necessary, a certified letter to the participant's last known mailing address or local equivalent methods). These contact attempts should be documented in the participant's medical record;
- Should the participant continue to be unreachable, the participant will be considered to have withdrawn from the study.

8. STUDY ASSESSMENTS AND PROCEDURES

8.1. Administrative Procedures

The investigator (or an appropriate delegate at the investigator site) must obtain a signed and dated ICD before performing any study-specific procedures.

Study procedures and their timing are summarized in the [SoA](#). Protocol waivers or exemptions are not allowed.

Adherence to the study design requirements, including those specified in the [SoA](#), is essential and required for study conduct.

All screening evaluations must be completed and reviewed to confirm that potential participants meet all eligibility criteria. The investigator will maintain a screening log to record details of all participants screened and to confirm eligibility or record reasons for screening failure, as applicable.

Every effort should be made to ensure that protocol -required tests and procedures are completed as described. However, it is anticipated that from time to time there may be circumstances outside the control of the investigator that make it unfeasible to perform the test. In these cases, the investigator must take all steps necessary to ensure the safety and well-being of the participant. When a protocol -required test cannot be performed, the investigator will document the reason for the missed test and any corrective and preventive actions that they have taken to ensure that required processes are adhered to as soon as possible. The study team must be informed of these incidents in a timely manner.

For samples being collected and shipped, detailed collection, processing, storage, and shipment instructions and contact information will be provided to the investigator site prior to initiation of the study.

The total blood sampling volume for individual participants in this study is approximately 225 mL in Part A, 150 mL in Part B, and 190 mL in Part C. The actual collection times of blood sampling may change. Additional blood samples may be taken for safety assessments at times specified by the sponsor, provided the total volume taken during the study does not exceed 550 mL during the study.

8.2. Efficacy Assessments

Efficacy assessments are not performed. PD activity is being measured at times specified in the [SoA](#).

8.2.1. Gluten Challenge

Participants are required to fast for at least 8 hours, except for water and any medications they might have previously been prescribed, prior to the study visits where GC are performed (see [SoA](#)).

- **Part A:** All eligible, enrolled participants will undergo GC at Day 15.
- **Part B:** All eligible, enrolled participants will undergo 1-day GC during run-in and at times as specified in the [SoA](#).
- **Part C:** All eligible, enrolled participants will undergo 1-day GC at times as specified in the [SoA](#).

In Part B, during run-in period: all participants must meet all inclusion criteria before commencement of GC except [Inclusion Criterion #5](#).

A qualified staff member will prepare the GC in bottles at times specified in the [SoA](#).

Participants will consume 9g of gluten protein PO in the clinic and avoid foods (only water is permitted) at least 30 minutes after completion of the gluten drink. The participant will be observed for at least 4 hours to monitor for hyperacute reactions requiring medical treatment and collection of biomarker samples.

Compliance with the GC is defined as completion of the entirety of the 9g GC, including container wash steps, within approximately 15 minutes. Participants will consume the GC on site under the observation of site staff.

Any symptoms associated with the GC should be recorded as AEs (See [Section 8.4](#)). Any AEs associated with the GC study assessment are separate to AEs related to study intervention (KAN-101/PBO).

8.2.1.1. Confirmation of Symptomatic Response to Run-in GC (Part B Only)

For [Inclusion Criterion # 5](#):

- Symptomatic response to the run-in GC is defined as at least 1 moderate to severe GI symptom (either diarrhea, abdominal pain, bloating, or nausea) on the day of the GC.

Either/or
- Symptom severity will be assessed using CDS D v2.1 scores on the day of the GC (see Section 8.2.3.1).

8.2.2. Plasma IL-2 Biomarker Assessment

Plasma samples will be collected to assess the magnitude of biomarker response of IL-2 pre- and post-GC in peripheral blood (Part A – exploratory endpoint; Part B and Part C – primary endpoint on Day 15 and secondary endpoints on Weeks 12, 24, and 36).

Further details are presented in [Section 8.7](#).

8.2.3. Patient Reported Outcomes

8.2.3.1. CDS D v2.1

The CDS D v2.1, a novel patient-reported outcome measure developed for use with patients with CeD, consists of five symptoms including diarrhea, abdominal pain, bloating, nausea, and tiredness. The CDS D v2.1 assesses severity, in five scales from “none” to “very severe”, and frequency. The CDS D v2.1 will be assessed daily as part of the eDiary beginning during the screening period after signing the ICD.

The CDS D v2.1 should be completed for at least a minimum of 7 consecutive days during screening at any time prior to the baseline visit (Day 1) in Part A and Part C and prior to run-in GC visit (Day -21) for Part B. After screening and through the end of the study, compliance with the CDS D v2.1 is defined as 80% completion.

8.2.3.2. PGIC

The PGIC is a patient-completed question to assess the overall impression of disease improvement experienced by the patient. The PGIC score ranges from “much better” to “much worse”. The PGIC will be assessed at visits specified in [SoA](#).

8.2.3.3. PGIS

The PGIS is a patient-completed question to assess the overall impression of disease severity experienced by the patient. The PGIS score ranges from “None” to “Very Severe”. The PGIS will be assessed at visits specified in [SoA](#).

8.2.4. Esophagogastroduodenoscopy With Biopsy (Biopsy Substudy Only)

As part of the biopsy substudy in Part B and Part C, EGD with biopsies will be collected from participants at applicable sites at times specified in the [SoA](#).

Urine pregnancy test may be performed prior to EGDC per local practice guidelines. EGD with biopsy will be performed by a qualified gastroenterologist at each site. All study gastroenterologists will be trained on the study-specific procedures for obtaining the biopsy, including the location and number of biopsies to be obtained, and procedures for storing and shipping of samples.

Approximately 6 duodenal biopsies will be obtained.

Endoscopy data obtained previously during screening up to 3 months prior to rescreening may be used as the baseline histology in a subject who has continued GFD and has not undergone a GC.

8.2.4.1. Histological Assessments (Biopsy Substudy only)

Tissue samples collected during biopsy as specified in the [SoA](#) will be analyzed for histological state (including, but not limited to: villus height, crypt depth, Marsh score, and IEL count) (see [Appendix 10](#)). Histology will be centrally read by qualified raters.

Management of Incidental Findings

An incidental finding is one unknown to the participant that has potential health or reproductive importance, which is discovered unexpectedly in the course of a research study, but is unrelated to the purpose and beyond the aims of the study.

Histology from EGD biopsy will be reviewed by a central review facility. The purpose of this review is to evaluate histology for celiac disease. Central histological review is not a complete medical review of the participant. If, during the central review process, an unexpected observation is identified and this finding could, in the opinion of the central reviewer, have a significant health or reproductive consequence, this finding may be shared with the study sponsor for disclosure to the PI. All follow-up testing and final diagnosis will be left to the discretion of the medical professionals at the site or those with an existing physician--participant relationship. The PI will be responsible for reporting any AEs identified from incidental findings as described in the AE reporting section. Identification of such incidental findings during the central review process should not be expected, and the site maintains responsibility for performing a general safety review of all histology as per site protocols.

8.3. Safety Assessments

Safety will be assessed through the monitoring of AEs, clinical signs and symptoms, vital signs and clinical laboratory evaluations.

All participants will be monitored continuously for AEs from screening until the safety follow-up visit on Week 52. AE severity will be assessed using the NCI CTCAE v5.0 or higher (see [Appendix 10](#)). The DSMB will review all SAEs and \geq Grade 3 AEs that are assessed to be related to study drug as these events may occur. Any Grade 4 AEs assessed as related to study drug will result in notification of the FDA in parallel with the DSMB.

Participants will be monitored in the clinic for 4 hours following IV study drug administration for IRR (see [Appendix 9](#)).

For Part A, the DSMB will review cumulative safety data by dose cohort before opening a higher dose cohort. DLTs are defined in [Section 4.1.1.1.1](#). Any DLT experienced during the Treatment period (Day 1 to Day 7) through Day 15 prior to GC will result in a pause in the study enrollment and a review of all available safety data by the DSMB prior to dosing any additional participants; further details for cohort stopping rules are presented in [Section 6.6.1.1](#).

In relation to participant safety during the COVID-19 pandemic, current national laws and local recommendations should be strictly adhered to during the study.

Planned time points for all safety assessments are provided in the [SoA](#). Unscheduled safety measurements may be obtained at any time during the study to assess any perceived safety issues.

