 - **Run-in period:** 21 days; eligible participants will undergo 1-day 9g GC on first day of run-in period (at least 21 days before administration of first dose of study drug) to confirm symptomatic response to oral GC.
 - **Treatment period:** 7 days; symptomatic responders to the run-in GC will be randomized 1:1:1:1 to 1 of the 4 treatment groups and administered study intervention IV for 3 administrations (1 administration every 3 days starting at Day 1).
 - **Observation/follow-up period:** 358 days, including post-dosing GC on Day 15 (to assess primary endpoint), post-dosing GC at Weeks 12, 24 and 36 (to assess exploratory endpoints) and follow-up visits on Day 28 and Week 52.
- **Biopsy Substudy** (at applicable sites only, up to approximately 50% of Part B cohort): includes collection of duodenal biopsies at screening and Week 52.
- **Part C** – Part C is a Phase 2, double-blind, PBO-controlled, parallel design study to compare the biomarker response (plasma IL-2; primary endpoint) following GC on Day 15. Safety, tolerability, and PK of KAN-101 in adult participants (18 to 70 years inclusive) with histology-confirmed CeD will also be evaluated. Participants will be randomized 1:1:1:1 and stratified by participation in biopsy substudy to the following treatment groups:
 - PBO (Group 1)
 - 0.6 mg/kg (Group 2)
 - 1.2 mg/kg (Group 3)
 - 3.0 mg/kg (Group 4)
- Initiation of Part C will occur following the DSMB review of available safety data from Part B and the sponsor's approval.

- Part C will have 3 periods and 1 substudy:
 - **Screening period:** Day -28 to Day -1
 - **Treatment period:** Day 1 to Day 7; eligible participants will be randomized 1:1:1:1 to 1 of the 4 Treatment Groups and administered study intervention IV for 3 administrations (1 administration every 3 days starting at Day 1).
 - **Follow-up period:** Day after last dose till Day 364 (± 3 days), including post-dosing GC on Day 15 (to assess primary endpoint), post-dosing GC at Weeks 12, 24 and 36 (to assess exploratory endpoints) and safety follow-up visits on Day 28 and Week 52.
- **Biopsy Substudy** (at applicable sites only, up to approximately 50% of Part C cohort): includes collection of duodenal biopsies at screening and Week 52.

Number of Participants:

Part A: up to 12 participants will be randomized.

Part B: Approximately 16 participants (approximately 4 participants per treatment group) will be randomized.

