4.4. End of Study Definition

The end of the study is defined as the date of the last visit of the last participant in the study or last scheduled procedure shown in the [SoA](#) for the last participant in the trial globally.

A participant is considered to have completed the study if they have completed all periods of the study, including the last visit or the last scheduled procedure shown in the [SoA](#).

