6. STUDY INTERVENTION(S) AND CONCOMITANT THERAPY

Study interventions are all prespecified investigational and noninvestigational medicinal products/auxiliary medicinal products, medical devices, and other interventions (eg, surgical and behavioral) intended to be administered to the study participants during the study conduct.

For the purposes of this protocol, study intervention refers to KAN-101 or PBO for KAN-101.

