8.4.1. Time Period and Frequency for Collecting AE and SAE Information

The time period for actively eliciting and collecting AEs and SAEs (“active collection period”) for each participant begins from the time the participant provides informed consent, which is obtained before undergoing any study-related procedure and/or receiving study intervention, through and including a minimum of 28 calendar days, except as indicated below, after the last administration of the study intervention.

Follow-up by the investigator continues throughout the active collection period and until the AE or SAE or its sequelae resolve or stabilize at a level acceptable to the investigator.

When a clinically significant AE remains ongoing at the end of the active collection period, follow-up by the investigator continues until the AE or SAE or its sequelae resolve or stabilize at a level acceptable to the investigator and the sponsor concurs with that assessment.

For participants who are screen failures, the active collection period ends when screen failure status is determined.

If the participant withdraws from the study and also withdraws consent for the collection of future information, the active collection period ends when consent is withdrawn.

If a participant permanently discontinues or temporarily discontinues study intervention because of an AE or SAE, the AE or SAE must be recorded on the CRF and the SAE reported using the CT SAE Report Form.

Investigators are not obligated to actively seek information on AEs or SAEs after the participant has concluded study participation. However, if the investigator learns of any SAE, including a death, at any time after a participant has completed the study, and they consider the event to be reasonably related to the study intervention, the investigator must promptly report the SAE to Pfizer Safety using the CT SAE Report Form.

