10.3.3. Recording/Reporting and Follow-Up of AEs and/or SAEs During the Active Collection Period

AE and SAE Recording/Reporting		

The table below summarizes the requirements for recording AEs on the CRF and for reporting SAEs on the CT SAE Report Form to Pfizer Safety throughout the active collection period. These requirements are delineated for 3 types of events: (1) SAEs; (2) nonserious AEs; and (3) exposure to the study intervention under study during pregnancy or breastfeeding, and occupational exposure.
 
It should be noted that the CT SAE Report Form for reporting of SAE information is not the same as the AE page of the CRF. When the same data are collected, the forms must be completed in a consistent manner. AEs should be recorded using concise medical terminology and the same AE term should be used on both the CRF and the CT SAE Report Form for reporting of SAE information.
		
Safety Event	Recorded on the CRF	Reported on the CT SAE Report Form to Pfizer Safety Within 24 Hours of Awareness
SAE	All	All
Nonserious AE	All	None
Exposure to the study intervention under study during pregnancy or breastfeeding	All AEs or SAEs associated with EDP or EDB Note: Instances of EDP or EDB not associated with an AE or SAE are not captured in the CRF	All instances of EDP are reported (whether or not there is an associated SAE)* All instances of EDB are reported (whether or not there is an associated SAE)**
Environmental or occupational exposure to the product under study to a nonparticipant (not involving EDP or EDB)	None. Exposure to a study nonparticipant is not collected on the CRF	The exposure (whether or not there is an associated AE or SAE) must be reported***

* EDP (with or without an associated SAE): is reported to Pfizer Safety using the CT SAE Report Form and EDP Supplemental Form; if the EDP is associated with an SAE, then the SAE is reported to Pfizer Safety using the CT SAE Report Form.
 
** EDB is reported to Pfizer Safety using the CT SAE Report Form, which would also include details of any SAE that might be associated with the EDB.
 
*** Environmental or occupational exposure: AEs or SAEs associated with occupational exposure are reported to Pfizer Safety using the CT SAE Report Form.
		

090177e19fcc12ed\Approved\Approved On: 30-Jan-2024 19:45 (GMT)

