- For each AE or SAE, the investigator **must** document in the medical notes that they have reviewed the AE or SAE and have provided an assessment of causality.
- There may be situations in which an SAE has occurred and the investigator has minimal information to include in the initial report to Pfizer Safety . However, **it is very important that the investigator always make an assessment of causality for every event before the initial transmission of the SAE data to Pfizer Safety.**
- The investigator may change their opinion of causality in light of follow-up information and send an SAE follow-up report with the updated causality assessment.
- The causality assessment is one of the criteria used when determining regulatory reporting requirements.
- If the investigator does not know whether or not the study intervention caused the event, then the event will be handled as “related to study intervention” for reporting purposes, as defined by Pfizer Safety. In addition, if the investigator determines that an SAE is associated with study procedures, the investigator must record this causal relationship in the source documents and CRF, and report such an assessment in the dedicated section of the CT SAE Report Form and in accordance with the SAE reporting requirements.

Follow-Up of AEs and SAEs

- The investigator is obligated to perform or arrange for the conduct of supplemental measurements and/or evaluations, as medically indicated or as requested by the sponsor/Pfizer Safety, to elucidate the nature and/or causality of the AE or SAE as fully as possible. This may include additional laboratory tests or investigations, histopathological examinations, or consultation with other healthcare providers.
- If a participant dies during participation in the study or during a recognized follow-up period, the investigator will provide Pfizer Safety with a copy of any postmortem findings, including histopathology.
- New or updated information will be recorded in the originally submitted documents.
- The investigator will submit any updated SAE data to Pfizer Safety within 24 hours of receipt of the information.

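### A serious complication of the Week 52 biopsy that appears after that visit need not be reported to the sponsor (Parts B and C)

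*Protocol*

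**What the plan says.** The Protocol synopsis says that the substudy in each of Parts B and C "includes collection of duodenal biopsies at screening and Week 52". In the schedules of activities (1.3.2 and 1.3.3) the second EGD is in the Week 52 column, Day 364 with a window of 3 days either side. That column is the last scheduled visit and also holds the final adverse-event check. Section 2.3.1 lists bowel perforation and duodenal hematoma as risks of the procedure.

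On monitoring, 8.3 says: "All participants will be monitored continuously for AEs from screening until the safety follow-up visit on Week 52". On completion, 4.4 says: "A participant is considered to have completed the study if they have completed all periods of the study, including the last visit"; the last scheduled procedure is the stated alternative.

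For the time after that, 8.4.1 says: "Investigators are not obligated to actively seek information on AEs or SAEs after the participant has concluded study participation". A report to the sponsor is compulsory if the investigator learns of an SAE "at any time after a participant has completed the study, and they consider the event to be reasonably related to the study intervention". Section 6 fixes the meaning of the term: "study intervention refers to KAN-101 or PBO for KAN-101".

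**The concern.** The substudy's most invasive procedure is placed at the point where safety follow-up stops, and the reporting rule that takes over is tied to the drug alone. A participant could go home after the Week 52 EGD and later present with a perforation. The investigator could learn of it, correctly attribute it to the biopsy, follow the protocol to the letter and have no duty to tell the sponsor. Nor is any contact scheduled that would find the event.

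What could be lost is part of the safety record of a research procedure in a study that, by 2.3.2, offers participants no individual health benefit. Endpoints, estimands and comparisons between arms are untouched.

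**Working it through.** The plan states no figure on this point, so the check sets the clauses side by side and adds day counts and a ceiling on the number of procedures.

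**1. When collection ends**
- The last dose is on Day 7. The minimum in 8.4.1 is 28 days after the last dose: 7 + 28 = Day 35.
- The second EGD is at Day 364, which is 364 − 7 = 357 days after the last dose and 364 − 35 = 329 days after Day 35. No collection period is counted from a procedure.
- The reading more favourable to the plan is 8.3, which carries monitoring to Week 52.
- If the EGD and the final check fall on the same day, follow-up is 0 days. If they are split across the window (Day 361 and Day 367), it is at most 367 − 361 = 6 days. The protocol does not fix their order.

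**2. Whether another clause requires the report**

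| Clause | What it covers | Does it reach a late SAE attributed to the biopsy? |
|---|---|---|
| 8.4.1, post-completion rule | SAEs considered related to KAN-101 or placebo | No |
| 8.4.1.1, SAE reporting | SAEs in the active collection period | No |
| 10.3.3, what applies "if the investigator determines that an SAE is associated with study procedures" | A mandatory report, but the section opens with requirements "for reporting SAEs on the CT SAE Report Form to Pfizer Safety throughout the active collection period" | Not on its stated scope |
| 10.3.3, unknown cause | SAEs whose relation to the drug the investigator cannot judge | No, the cause is judged to be the biopsy |
| 8.4.1 and 8.4.3, continued follow-up | Events already identified | No |
| 10.3.4, after the electronic tool is off-line | Says the site *can* use a paper form or telephone | Permits, does not oblige |
| 10.1.1, IRB/EC notification | As the IRB/EC's own procedures require | Not a report to the sponsor |

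Attribution to the drug is an unlikely fallback. The longest mean half-life quoted in 4.2.1 is 36.8 minutes, so five half-lives are 5 × 36.8 = 184 minutes, about 3.1 hours, against a gap of 357 days. The protocol also keeps procedure and drug causality apart elsewhere: 8.2.1 treats events from the gluten challenge as distinct from drug-related events.

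**3. How the plan treats comparable moments**
- Infusions carry 4 hours of observation in the clinic (8.3), and gluten challenges at least 4 hours (8.2.1). Section 8.2.4 sets no observation or contact after the EGD.
- The screening biopsy must be at least 4 days before the run-in challenge (Part B) or first dose (Part C), with adverse events collected from consent onward. The Week 52 biopsy has no such guaranteed interval.

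**4. How many procedures**
- Ceiling from 9.5, at applicable sites: 0.5 × 104 = 52 in Part C and 0.5 × 16 = 8 in Part B; 52 + 8 = 60.
- Attrition is not given. As an assumption, 10%, 20% and 30% over 52 weeks give 60 × 0.9 = 54, 60 × 0.8 = 48 and 60 × 0.7 = 42.
- One unreported event would be 1/60 = 1.7%, 1/54 = 1.9%, 1/48 = 2.1% or 1/42 = 2.4% of the Week 52 EGDs. This scales a single event. It does not estimate how many to expect.

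**The case against.** The best counter-argument is that the protocol does treat procedure-related SAEs as reportable. Section 10.3.3 says so in mandatory terms and is set aside here only because of its heading and opening text. The *can* in 10.3.4 may describe a choice of channel rather than a choice whether to report. Section 8.4.1 sets only a minimum period, and no sentence says that active collection closes at the Week 52 visit. On this view the text is ambiguous and needs no more than clarification.

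Two practical points add to it. The protocol names the complications but does not say that they appear late. And the study was terminated: the Part B and Part C SAPs (both 6.3.7) drop the biopsy endpoints, and the EGD row has no entry under early termination, so few Week 52 procedures may have taken place.

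The practical points stand as limits on size. Other safeguards also narrow the gap: events seen by the visit are followed, unscheduled visits are allowed, and participants hold the investigator's contact details (10.1.11). The textual argument does not close it. Section 8.4.1 has a specific rule for the time after completion, 4.4 places completion at the last visit or procedure, and that rule names only the study intervention. Nothing extends collection past that point. A reader who follows the specific rule is not in breach, even if a more generous reading is possible.

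**Conclusion.** The concern holds. As written, an SAE that first appears after the Week 52 visit and is attributed to the biopsy carries no duty of report to the sponsor, and no scheduled contact would find it.

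The scope is small: at most about 60 procedures, 42 to 54 under the assumed attrition, and possibly far fewer given termination. The documents do not say how many were done. The conclusion rests on reading 10.3.3 within its stated scope and on the Section 6 definition of study intervention. Zero days of follow-up is the least the schedule allows, not a certainty. Because the documents give no complication rate or time to onset, the finding concerns a missing duty and predicts no number of missed events.

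**What to change.** 1. In the last paragraph of Protocol 8.4.1, widen the condition so that it covers SAEs reasonably related to the study intervention *or to a study procedure*.
2. In the Part B and Part C schedules of activities, add a note for biopsy-substudy participants: a closing adverse-event check, by telephone if needed, a few days after the Week 52 EGD, with active collection ending at that check. The sponsor should set the interval on clinical grounds, since the documents offer none.

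The cost is one wording change, one schedule note and one extra contact for each participant who has the Week 52 EGD. Dosing, endpoints, sample size and analysis stay as they are, and no new SAP output is needed.
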